Study size: We expect to include at least 3.2 million individuals who are included in the key target groups for seasonal influenza vaccination across the 3 Nordic countries. All available data within

countries will be used and the statistical power of our proposed study will be reflected in the 95% CIs of the effectiveness estimates.

Data analysis: Using target trial emulation, vaccinated and unvaccinated cohorts will be compared in matched (1:1) survival analyses to estimate IVE while adjusting for potential confounders. The start of follow-up for matched pairs will be defined as day 14 after vaccination to ensure full immunisation. Sensitivity analyses will include use of negative control outcomes, regression discontinuity analysis, adjustments for prior event rates, and a test-negative case-control design on Danish data (negative test results are currently only available in Denmark).

The findings are aimed at informing regulatory decision-making and vaccination strategies ahead of the 2025-2026 influenza season.

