The Danish Microbiology Database	Information on positive results of RT-PCR tests for influenza are obtained from The Danish Microbiology Database (MiBa) which holds information on all microbiology samples analysed at Danish departments of microbiology, including information on influenza test results, date of sampling, date of analysis, type of test and interpretation of the test (positive / negative).	Register	Nationwide	2020 – today	Daily	No lag	(27)

Country	Details of the individual-level data sources						
Finland							
Title	Info	Type	Setting	Study availability	Update	Lag	Ref
Finnish Population Information System	The register is held by the Digital and Population Data Services Agency and contains personal data on all permanent residents in Finland such as the unique personal identifier, date of birth, place of residence, date of death, and date of immigration, and emigration.	Register	Nationwide	1964 - today	Daily	No lag	(28)
National Vaccination Register	The register, which is based on the Register of Primary Health Care Visits, holds information on almost all influenza vaccinations administered in Finland; only influenza vaccinations given by social care givers such as nursing homes might be incompletely covered. Data include the date of vaccination, vaccine batch number and trade name.	Register	Nationwide	2009 - today	Daily	No lag	(29)

Care Register for Health Care	The register comprises information on all in-hospital care (since 1969) and outpatient specialist care (since 1998) in Finland, including admission and discharge dates, whether hospitalisation was planned or acute, codes for discharge diagnoses (according to ICD-10) and surgical procedures, whether discharged as deceased, to own private residence or other health care facilities, type of department and hospital. The register is held by the Finnish Institute for Health and Welfare.	Register	Nationwide	1967 - today	Daily	1-4 weeks	(30)
Register for Primary Health Care Visits	The register is held by Finnish Institute for Health and Welfare and holds data on all primary health care services delivered in Finland.	Register	Nationwide	2011 - today	Daily	No lag	(31)

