9.8 Supplementary analyses and quality control

Confounding-by-indication and healthy vaccinee bias are critical methodological concerns in studies of influenza VE. (46). Confounding by indication would result in an underestimate of true effectiveness if individuals with comorbidities that increase the risk of the study outcome are more likely to get vaccinated. Healthy vaccinee bias occurs when healthy individuals are more likely to get vaccinated while the most frail and sick elderly with the highest risk of the study outcome are not vaccinated, especially at the end of life. In Table 8 below, we present the key possible confounders in studies of effectiveness and how they are likely to be associated with study exposures and outcomes.

Table 8. List of possible confounders in IVE studies

Possible Confounder	Influenza vaccination propensity	Influenza hospitalisation risk	All-Cause Mortality risk	Bias Direction for VE against	Bias direction for VE against

				influenza hospitalisation	all-cause mortality
Comorbidity	↑	↑	↑	Underestimate	Underestimate
High frailty	↓	↑	↑	Overestimate	Overestimate
Healthcare seeking	↑	↑	↓	Underestimate	Overestimate
Healthcare access	↑	↑	↓	Underestimate	Overestimate

The current state-of-the-art in observational vaccination effectiveness estimation is comprised mainly of two study approaches, the test-negative design and TTE. Both approaches seek to mitigate the impact of bias and confounding. Guilin and colleagues (47) evaluated the performance of the two approaches in the evaluation of Covid-19 VE estimation. In data with rich covariate information, they observed similar VE estimates from the two methods. In data with only a few covariates, the test-negative design tended to overestimate the VE, while the target trial emulation underestimated the VE.

To evaluate the potential for biases by healthcare-seeking behaviour or healthcare access, the TTE will be supplemented by a TND study. The TND study is only feasible in Denmark due to lack of test-negative results in Finland and Sweden. Moreover, supplementary analysis comprising of PERR, RDA, and Negative Control Outcomes Analyses will be conducted to allow for comparison and contextualisation of results. Moreover, to strengthen the robustness of findings, triangulation—integrating evidence from multiple analyses with different methodologies—can provide valuable insights into potential biases and enhance the interpretation of results.

Test-Negative Case Control design

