The test-negative case-control (TNCC) study design is a variant of the case-control method specifically developed for evaluating VE. (48) Due to unavailability of test negatives data in Finland and Sweden, we will conduct a TNCC study on Danish data only. In this approach, cases are individuals who test positive for influenza, while controls are those who test negative. The TNCC design offers several methodological strengths. It reduces bias from healthcare-seeking behaviour, as both cases and controls sought care and allows for efficient VE estimation during the influenza season. However, the TNCC design also has important limitations. It assumes that influenza vaccine does not affect the risk of other, non-influenza respiratory infections. (48) The design may be subject to bias if cases and

controls differ in disease severity. (49) Moreover, as the use of electronic healthcare records, including register-based data, for identifying cases and controls might cause bias (e.g., misclassification), and active enrolment of study participants is ideal in the TNCC design. (50) However, this increases the cost of the TNCC studies and limits its practicality to estimate VE against rare outcomes. Since a core assumption of the TNCC design is similar healthcare seeking behaviour among those who get tested, there is potential for selection bias if testing practices vary by vaccination status or other patient characteristics.

In the Danish population of individuals who were PCR-tested for influenza during the 2024–2025 season, we will employ a TNCC design to estimate the vaccine effectiveness against influenza infections during the 2024–2025 influenza season. We will exclude negative tests within 7 days of a previous negative test and within 21 days of a subsequent positive test. All tests within 90 days of a previous positive test will be excluded as these likely represent the same episode. Individuals can contribute with a maximum of one negative PCR test, which will be selected at random.

Patients will be considered vaccinated if they received an influenza vaccine at least 14 days before the PCR sample date. Patients will be considered unvaccinated if they have not received the influenza vaccine on the PCR test date or if they have received the influenza vaccine within two weeks before the PCR test date.

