The main assumption is that, aside from the jump in vaccination likelihood at age 65, individuals just below vs. just above 65 should be comparable in terms of health and risk factors. To check this, we will inspect covariate distributions around the cut-off. We also expect to observe a noticeable “jump” in vaccination rates at age 65. If we do not observe this jump, it may indicate that the vaccination policy recommendation has weak influence, and the instrument’s strength may be inadequate.

Testing frequency

Tracking the frequency of influenza testing among vaccinated and unvaccinated individuals during follow-up provides insights into residual healthcare utilization or access bias. Testing rates can be compared between the groups to identify discrepancies that could influence VE estimates. We will assess testing frequency among vaccinated and unvaccinated individuals and stratify by calendar month to evaluate whether they are consistent across both groups and months, or driven by specific factors (e.g., timing patterns in a situation of increased testing activity during high influenza season). Ideally, we want the testing frequency to be similar. The results will be presented as the number of tests per group and calendar month, in a table or a graph. These steps ensure that any observed associations between vaccination and outcomes are not unduly influenced.

Sensitivity analysis before full immunization

We will conduct a sensitivity analysis using the primary cohort design (TTE approach) to evaluate vaccine effectiveness (VE) with an alternative time zero. The objective is to determine whether there is a difference in the incidence of influenza hospitalizations when time zero is set at the day of vaccination (Day 0) versus the day of full immunization (Day 14). Accordingly, we will estimate VE for the period from Day 0 to Day 14, and from Day 0 until the end of follow-up, to assess any potential effect of early events on our vaccine effectiveness estimates.

Quality control

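### The testing-frequency check counts all influenza tests, including the positive ones that are a primary outcome, so similar counts do not show similar test-seeking; nor is the check limited to Denmark, the only country with negative results

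*Protocol*

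**What the plan says.** The Testing frequency part of section 9.8 introduces the comparison as one that "provides insights into residual healthcare utilization or access bias". It then sets out three things.

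- **Measure:** "We will assess testing frequency among vaccinated and unvaccinated individuals and stratify by calendar month", and "The results will be presented as the number of tests per group and calendar month, in a table or a graph". Positive and negative tests are not separated.
- **Criterion:** "Ideally, we want the testing frequency to be similar".
- **Conclusion:** the closing sentence says that these steps ensure that the observed associations are free of undue influence.

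No country is named in this part. Elsewhere the protocol is clear about which countries hold negative results. The abstract says that "negative test results are currently only available in Denmark". Section 9.8 says that "The TND study is only feasible in Denmark due to lack of test-negative results in Finland and Sweden", and restricts the test-negative analysis accordingly: "Due to unavailability of test negatives data in Finland and Sweden, we will conduct a TNCC study on Danish data only". That Danish analysis has its own monthly plot of testing by vaccination status, also not split by result.

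Table 7 in section 9.4 describes the Danish Microbiology Database as holding test interpretations of both kinds. It describes the Finnish and Swedish sources as registers of confirmed or notified infections. Laboratory-confirmed influenza is a primary outcome in Table 1.

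**The concern.** The check is meant to show whether vaccinated and unvaccinated people differ in how readily they are tested, because such a difference would distort VE against laboratory-confirmed influenza. A useful measure should respond to test-seeking and not to the effect of the vaccine.

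The planned count responds to both. Every influenza illness that the vaccine prevents removes a test from the vaccinated group, so equality of total tests is not what equal test-seeking would produce.

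The two influences can also cancel. Table 8 expects healthcare seeking to go with vaccination and to bias VE against influenza hospitalisation downwards. More testing among the vaccinated raises their count while an effective vaccine lowers it. The check can therefore look reassuring when the bias that the protocol itself anticipates is present.

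The missing country limit adds a second problem. Where only positives are recorded, a count of tests is a count of outcome events and says nothing separate about test-seeking.

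**Working it through.** The protocol gives no expected number of tests, so there is no figure to reproduce. What can be checked is the ratio that the planned measure would show under known conditions.

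**Inputs**
- VE: 24% (Stockholm) and 33% (Finland) in people aged 65 and over in 2016–2017, and 47% pooled for older adults in matched epidemic seasons. All are cited in section 7.
- p, the share of tests that are positive in the unvaccinated: not in the protocol; assumed at 5% to 40%.
- r, test-seeking in the vaccinated relative to the unvaccinated: 1 means equal; 1.10 is used as an example.
- Assumption: vaccination does not change the risk of non-influenza respiratory illness.

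**Formulas** (expected vaccinated/unvaccinated ratio)
- All tests: r × [(1 − p) + p × (1 − VE)] = r × (1 − p × VE)
- Positive tests only: r × (1 − VE)
- Negative tests only: r

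**Equal test-seeking (r = 1), all tests**

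| VE | p = 5% | 10% | 20% | 30% | 40% |
|---|---|---|---|---|---|
| 24% | 0.988 | 0.976 | 0.952 | 0.928 | 0.904 |
| 33% | 0.984 | 0.967 | 0.934 | 0.901 | 0.868 |
| 47% | 0.977 | 0.953 | 0.906 | 0.859 | 0.812 |

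The negative-test ratio is 1.00 in every cell. Along a row, the all-test ratio falls as positivity rises. A table by calendar month would therefore show a trend with no change in behaviour.

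**Masking.** Let the vaccinated seek testing 10% more often, with p = 30% and VE = 33%.
- All tests: 1.10 × (1 − 0.30 × 0.33) = 1.10 × 0.901 = 0.991, which reads as similar.
- Negative tests: 1.10, which shows the difference.
- Apparent VE against confirmed infection: 1 − 1.10 × 0.67 = 0.263, about 26% instead of 33%.

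The excess test-seeking that equal totals would hide is 1/(1 − p × VE) − 1:
- p = 5%, VE 24%: 1/0.988 − 1 = 1%
- p = 10%, VE 47%: 1/0.953 − 1 = 5%
- p = 30%, VE 24%: 1/0.928 − 1 = 8%
- p = 40%, VE 47%: 1/0.812 − 1 = 23%

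**Positives only, conditional on the check being run in Finland or Sweden.** With r = 1 the ratio is 0.76, 0.67 and 0.53 for VE of 24%, 33% and 47%. That is 1 − VE restated.

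**The case against.** **Country.** A reader might infer that tests will be counted in all three countries, since the part carries no Danish restriction and section 9.6 has common scripts run in each country. The protocol does not say so. It states repeatedly that negative results exist only in Denmark, and its other testing plot belongs to the Danish analysis, so a Danish-only intention is quite possible. What stands is that the scope is unstated. The Finnish and Swedish ratios above describe a count that may never be made.

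**Size.** A reader might also infer that an effective vaccine will always look like marked differential testing. At 5–10% positivity the shift is only about 1–5%, so in low-positivity months the planned comparison is nearly undistorted. The problem matters at higher positivity, and those are the months in which most confirmed cases would be expected.

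**Weight.** The wording is partly cautious, there is no threshold or decision rule, and the test-negative study and negative control outcomes also address healthcare seeking. That is fair, and it limits the consequences. It does not make the stated ideal the right one, or support the closing claim.

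**Level of detail.** Tabulation by result and person-time denominators are often left to an analysis plan. Here, however, the protocol itself fixes the measure, the criterion and the conclusion, and the three do not fit together.

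**The alternative.** Negative tests are a neutral marker only if vaccination leaves other respiratory infections unaffected. The protocol names this as a limitation of the test-negative design, and it must be named here too.

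**Conclusion.** The point holds for the measure whichever countries are meant. Total tests include the primary outcome, so the expected ratio under equal test-seeking is 1 − p × VE. At VE of 24–47% this is about 0.95–0.99 for p of 5–10% and 0.81–0.93 for p of 30–40%. Similar totals can conceal more test-seeking by the vaccinated.

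The size rests on assumed positivity, on the cited VE values applying to this season, and on no vaccine effect on other respiratory infections. On country, the finding is only that the check is not limited to Denmark, where alone it can be done.

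This is a supplementary diagnostic. It would be wrong to infer that any primary or secondary VE estimate is changed by it. What changes is how far the diagnostic can support those estimates, which makes the correction worthwhile but not critical.

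**What to change.** In section 9.8, Testing frequency:

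1. State that the check uses Danish data only, and that differential testing cannot be checked in Finland and Sweden.
2. Make the influenza-negative test rate per person-time in the matched cohort the measure of differential testing: vaccinated versus unvaccinated rate ratio with 95% CI, by calendar month. Show all tests descriptively.
3. Name the assumption that vaccination does not affect non-influenza respiratory infections.
4. Replace the verb ensure in the closing sentence with wording that claims only an assessment.

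Split the monthly plot in the Danish test-negative analysis by result in the same way.

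The cost is a few sentences and one extra tabulation from Danish results already needed for the test-negative study. The downside is that no testing check can be claimed for Finland and Sweden.

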9.9 Limitations of the research methods

The statistical power of brand-specific estimates may be limited for the vaccines that are less frequently procured, hence used, in a given country. The statistical precision of our estimates will depend on the seasonal incidence of infections which varies and the uptake of the different influenza vaccine brands.

Cohort studies are susceptible to confounding due to differences in vaccinated persons compared to unvaccinated persons. Confounding due to differences in healthcare seeking behaviour, or to differences in risk of severe disease, can be substantial and can challenge the estimation of the true vaccine effect. We will assess the possible impact of confounding carefully by implementing different supplementary analyses each with unique strengths and weaknesses allowing for triangulation of our findings to support a nuanced interpretation of the results.

Due to only regional availability of influenza vaccination data in Sweden, the majority of the study population is expected to be from Denmark and Finland. We expect near-real time data availability from Denmark and Finland. In Sweden we expect to be able to receive data at one time point – timed later in the data analysis process to ensure that the largest number of influenza vaccinated is included and we have a full representation of the influenza season, without delaying reporting of results.

The timing of vaccination relative to influenza virus circulation can influence VE estimates. Individuals vaccinated earlier or later in the season might experience different levels of exposure to circulating viruses, leading to time-related heterogeneity in effects that is not represented by our VE estimates.

10. PROTECTION OF HUMAN PARTICIPANTS

No individual-level data will be shared between parties. Country-specific analyses are conducted on pseudo-anonymized data. All parties adhere to GDPR.

11. MANAGEMENT AND REPORTING OF ADVERSE EVENTS/ADVERSE REACTIONS

Not applicable. Secondary use of data.

12. PLANS FOR DISSEMINATING AND COMMUNICATING STUDY RESULTS

Main results expected in the final study report:

- Baseline characteristics tables, including prior to matching and after matching, of two separate cohorts of 65+-year-olds (trial 1) and 18-64 years-of-age at increased risk (trial 2)
- Figures of cumulative incidence curves for vaccinated and unvaccinated, per country, outcome, brand and trial
- Brand-specific effectiveness estimates-tables with stratified analyses (age, sex, comorbidity, Covid-19 status, influenza vaccination history)
- Supplementary analyses results

We anticipate one manuscript, and findings will be reported to the general public by institutional press releases upon acceptance in academic peer-review journals or upon uploading to a pre-print server (if decided relevant to do so). The study protocol and study report deliverables will be made public in the HMA-EMA Catalogue of RWD studies when approved by EMA. We will adhere to the STROBE and ENCePP guidelines for the conduct of observational studies and for scientific independence and transparency.

